## 1. Introduction/Objective

The proposed study will examine the efficacy of Pneumoglide on facilitating the process of endotracheal intubation while it prevents injury to the upper teeth and aspiration of gastric contents into the lungs. These two complications are among common mishaps during endotracheal intubation by less experienced operators.

## 2. Subjects/Methods/Data Collection

This study will be a prospective clinical trial of patients who will receive general anesthesia with endotracheal intubation for their surgery. All patients undergoing general anesthesia and assigned to be anesthetized by an anesthesia team that includes a PGY-2 or PGY-3 residents will be screened for enrollment. All patients with recognized as difficult intubation or with obvious anatomical deviation of their airway (congenital or cancer-related) will be excluded. After initial screening and signing an informed consent, patients will be randomized into two groups: Group I will be intubated with while Pneumoglide device is used and Group II will be intubated in a conventional method without using Pneumoglide device. The primary endpoint of the study will be the success of the intubation by the trainees, The secondary outcome variables will include the number of the attempts to intubate the trachea, the time it lapse from the reaching to the laryngoscope device until the time the trachea is intubated and the correct placement of the endotracheal tube is verified. Additionally, we will collect all cases the required assistance from the attending staff in either group. Among patients in group I, the grade of vocal cord visualization will be documented with direct laryngoscopy with Macintosh blade 3-4 before inserting Pneumoglide and after insertion of the device. In group II, this variable will not be collected. Collected data will soon be entered into an Excel worksheet and will be saved in an approved Share Point folder allocated to this project. A copy of the informed consent and HIPPA waiver will also be saved in this folder. Access to this folder is granted for the authorized personnel and for the Ethics officer for auditing purposes.

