## 3. Data Analysis

There is currently no available data with the use of this device, therefore, we were unable to do a power analysis for sample size determination. This study is therefore considered a pilot project and the results obtained from this study can be used for sample size determination in future clinical trials.

Data will be analyzed quantitatively using VA approved programs, located at Dr. [name]'s office. Following removal of patients' identifiable information except for age and the date of procedure, the data will be transferred to an SPSS worksheet that is installed on a MacBook Pro located at [name] (204C) for further statistical analysis. The output files of the analyses will then reloaded to the Share Point folder and will remain there for future access by the authorized study team members.

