## 5. Benefits

This study will benefit both future patients of the VA as follow:

- a. Facilitating intubation by improving visualization of the airway (glottis)
- b. Decrease the risk of injury to the teeth, lips and oral mucosa by adding another protective layer
- c. Decrease the risk of gastric aspiration by occluding the esophageal opening while placing the endotracheal tube.

Data Collection tool (Excel Worksheet)

Name	Date	Group	Age	MP	preLG	PostLG	Success	#Att	TTI	FHelp	EsoInt	Inj	GasAsp
Case1													

Variable information:

Name: (Name+Last4)

Date: mm-dd-yy

Group: Device group

Age: years

MP: Mallampathi Classification of the airway

PreLG: Laryngeal grade before insertion of Pneumoglide

PostLG: Laryngeal grade after insertion of Pneumoglide

Success: Successful intubation by the trainee

#Att: Number of the attempts to successfully intubate

TTI: Time to intubate (minutes)

FHelp: Help from the faculty staff

EsoInt: Inadvertent esophageal intubation

Inj: Injury to the lips, teeth and oral mucosa

GasAsp: Gastric Aspiration

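### Eligibility is set by team, and no step fixes which trainee will intubate before the arm is known, so operator choice could depend on the arm

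*Combined protocol and SAP*

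**What the plan says.** Section 1 ties the clinical problem to operator experience: "These two complications are among common mishaps during endotracheal intubation by less experienced operators".

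The eligibility rule in section 2 is a property of the team. Patients are considered if they are "assigned to be anesthetized by an anesthesia team that includes a PGY-2 or PGY-3 residents will be screened for enrollment". Allocation comes next: "After initial screening and signing an informed consent, patients will be randomized into two groups". One arm uses the device; the other does not: "Group II will be intubated in a conventional method without using Pneumoglide device". No blinding or concealment of the allocation is described, and an operator cannot be unaware of a device being inserted.

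The primary endpoint depends on the operator: "The primary endpoint of the study will be the success of the intubation by the trainees". The data sheet printed at the end of section 5 codes it as "Success: Successful intubation by the trainee". Attending involvement is recorded as help: "we will collect all cases the required assistance from the attending staff in either group".

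The plan does not say which trainee in the team makes the first attempt, does not require that person to be named before the arm is known, and does not say how a case is scored if no trainee attempts. The data sheet has no column for operator, PGY level or experience.

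**The concern.** Randomising patients balances patient characteristics. It balances operator skill only if the operator is settled independently of the arm. If the team learns the arm first and then decides who takes the laryngoscope, operator skill becomes something that happens after randomisation. It can then differ systematically between arms, and enrolling more patients does not remove that difference.

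The plan's own rationale is that experience matters for intubation mishaps, so the primary endpoint is exposed. So are number of attempts, time to intubate and faculty help. Because the sheet records nothing about the operator, such a difference could be neither seen nor adjusted for. Adding an operator column would make it visible but would not prevent it; naming the operator before allocation would.

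**Working it through.** **Reading the text.** The team is assigned at screening, before randomisation, so any freedom to choose lies within that team or in staff changes. Three routes are left open by the text:

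1. The team holds two or more trainees of different seniority, and one is picked after the arm is known.
2. A trainee is swapped after the arm is known.
3. The attending steps in before any trainee attempt, leaving trainee success without a defined value.

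The documents neither state nor exclude any of these.

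**Size.** The plan gives no success rates, sample size, significance level or effect size, so there is no stated figure to reproduce. The inputs below are assumptions used to show scale.

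- Success with a PGY-2 operator, p2 = 75%; with a PGY-3 operator, p3 = 90%; no device effect.
- PGY-3 share s = 50% in one arm, and 50%, 55%, 70% or 90% in the other.

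Expected success in an arm = (1 − s) × p2 + s × p3. The spurious difference between arms therefore equals (difference in s) × (p3 − p2). The fraction of PGY-2 cases that must be switched to reach a share s is (s − 0.50) / 0.50.

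| PGY-3 share in the shifted arm | Expected success | Spurious difference from 82.5% | PGY-2 cases switched |
|---|---|---|---|
| 50% | 0.50 × 75 + 0.50 × 90 = 82.50% | 0 | 0% |
| 55% | 0.45 × 75 + 0.55 × 90 = 83.25% | 0.75 points | 0.05/0.50 = 10% |
| 70% | 0.30 × 75 + 0.70 × 90 = 85.50% | 3 points | 0.20/0.50 = 40% |
| 90% | 0.10 × 75 + 0.90 × 90 = 88.50% | 6 points | 0.40/0.50 = 80% |

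**Range over the assumed skill gap**, using gap × imbalance:

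| Skill gap | Imbalance 5 points | 20 points | 40 points |
|---|---|---|---|
| 10 points | 0.5 | 2 | 4 |
| 20 points | 1 | 4 | 8 |
| 30 points | 1.5 | 6 | 12 |

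**Effect on a test.** The plan specifies no test and no number of patients. As an illustration, take a two-sided 5% pooled two-proportion z-test (normal approximation) with 25, 50 or 100 patients per arm and senior success of 90%. With a 20-point gap and junior operators in 40% against 60% of cases (82% against 78% success), it would reject 6.4%, 7.9% and 10.9% of the time with no device effect. With 30% against 70% (84% against 76%), the figures are 10.8%, 16.9% and 29.2%. With the same operator mix in both arms, the spurious difference is 0 and the rate stays at 5%.

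**The case against.** Four arguments on the other side deserve weight.

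- **A trainee is meant to intubate.** The primary endpoint, the Success column, the recording of faculty help and the account in section 4 of novice trainees working under direct attending supervision all point the same way. A reader might infer from the eligibility sentence alone that the attending could routinely go first and that the question about less experienced operators would be missed. The documents read together do not support that. One could compute that attending-first cases in 5% to 10% of one arm, scored as trainee failures, would cost that arm 4 to 8 points (0.05 to 0.10 × 82.5%). That rests on the unsupported reading and is not offered as the likely size.
- **There may be one resident per team.** The wording of the rule is compatible with this. If it is so, and staff are not swapped, the trainee is in effect fixed before randomisation and the switch between residents disappears. This stands as a condition on the concern.
- **The larger figures need much switching.** Three points needs 40% of PGY-2 cases in one arm to change hands, and 6 points needs 80%. At 10% switching the difference is 0.75 points. Nor do the documents say which arm would attract the senior operator. This stands.
- **It is a pilot.** Section 3 says so: "we were unable to do a power analysis for sample size determination". That lowers the weight of any single test. But the same section offers the results as a basis for sizing future trials, so a distorted difference would be carried forward.

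**Conclusion.** The gap is real and conditional. The plan randomises to a visible intervention, has an endpoint that depends on the operator, and does not fix the operator before the arm is known. The text supports saying that operator choice can depend on the arm if teams hold more than one trainee, staff can be swapped, or the attending may step in before a trainee attempt. It does not support saying that this will happen.

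On an assumed 15-point skill gap the spurious difference runs from 0.75 points (modest switching) through 3 to 6 points (heavy switching). A reader might take the upper figures as the expected bias; nothing in the documents makes them typical, since the rates, shares and direction are all assumed. That the allocation is open is likewise inferred from the visible device and the absence of any blinding text. The point is a cheap improvement that protects the primary comparison, and does not show that the comparison is invalid.

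**What to change.** In section 2:

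- Change eligibility to patients for whom a PGY-2 or PGY-3 resident is the designated first laryngoscopist.
- Record that resident and the PGY level on the case record before the allocation is revealed, and log any later change of operator with its reason.
- Analyse every case in its randomised arm. Score the primary endpoint as success by the named resident, with no attempt counted as not a trainee success.
- Report the number of non-attempts and their reasons by arm, and add a sensitivity analysis restricted to cases that the named resident attempted.

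The scoring rule gives every randomised case a value, but unequal non-attempts would still lower one arm's rate. The restricted analysis selects on an event after randomisation. The two should therefore be read together with the counts by arm.

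The cost is one changed sentence, one entry per case and occasional logged staffing changes. The attending's freedom to intervene is unchanged.

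### The trainee is not recorded, so the primary comparison can only treat cases as independent, and its interval can be too narrow for conclusions about trainees in general if the device effect varies between them

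*Combined protocol and SAP*

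**What the plan says.** Section 2 defines the endpoint by what the trainee achieves: "The primary endpoint of the study will be the success of the intubation by the trainees". Eligible patients are those "assigned to be anesthetized by an anesthesia team that includes a PGY-2 or PGY-3 residents will be screened for enrollment". Allocation is by patient ("patients will be randomized into two groups"), and no ratio, blocking or stratification by trainee is stated.

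The data collection tool printed after Section 5 has one row per case and 14 columns: Name, Date, Group, Age, MP, preLG, PostLG, Success, #Att, TTI, FHelp, EsoInt, Inj and GasAsp. The primary outcome is defined there as "Success: Successful intubation by the trainee". No column identifies the operator.

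On analysis, Section 3 says "Data will be analyzed quantitatively using VA approved programs". It names no test, model or interval. There is no target number of patients ("we were unable to do a power analysis for sample size determination"). The stated use of the study is that "the results obtained from this study can be used for sample size determination in future clinical trials". The number of trainees and of cases per trainee is not given.

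**The concern.** Success depends on both the patient and the operator, and one resident is likely to intubate several study patients. With an unfamiliar hand-held device, some residents may gain more from it than others. If so, a conclusion about residents generally rests on how many residents were sampled as well as on how many patients. A case-level standard error leaves that component out.

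Two things are at stake. The first is the precision claimed for the primary comparison, since Section 1 motivates the study by complications among operators with less experience, a wider group than the residents who happen to take part. The second is the pilot's declared purpose. Variation in the device effect between trainees is a planning quantity for a later trial, and enrolling more patients per trainee does not remove it. A file without a trainee identifier cannot supply it.

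**Working it through.** The plan has no sample size, alpha or power to reproduce, so every numerical input below is an assumption.

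**Notation.** J trainees with m cases each, N = J × m, allocation 1:1. p0 and p1 are the success rates without and with the device. sa is the SD between trainees in baseline success, and sb the SD between trainees in device effect (both on the probability scale, taken as uncorrelated).

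**Variance of the difference in success proportions, patients randomised without regard to trainee.**
- Case-level variance: 2[p0(1−p0) + p1(1−p1)]/N.
- True variance over a population of trainees: case-level variance + sb²(m−1)/N.
- The sa term cancels. Differences in skill alone do not make the case-level interval too narrow.
- With one case per trainee (m = 1) or a constant effect (sb = 0), the excess is zero.
- The excess equals sb²(m−1)/(J × m), which tends to sb²/J as m grows. Only more trainees reduce it.

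**First set of assumptions: p0 = 0.70, p1 = 0.85.** The case-level variance is 2[0.21 + 0.1275]/N = 0.675/N, so true SE / case-level SE = √(1 + sb²(m−1)/0.675). For 5 trainees × 20 cases with sb = 0.15: √(1 + 0.0225 × 19/0.675) = √1.633 = 1.28. Actual coverage of a nominal 95% interval is 2Φ(1.96/ratio) − 1.

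| Trainees × cases | sb = 0.05 | sb = 0.10 | sb = 0.15 |
|---|---|---|---|
| 10 × 4 | 1.01 (94.9%) | 1.02 (94.5%) | 1.05 (93.8%) |
| 5 × 8 | 1.01 (94.7%) | 1.05 (93.8%) | 1.11 (92.2%) |
| 10 × 10 | 1.02 (94.6%) | 1.06 (93.4%) | 1.14 (91.4%) |
| 5 × 20 | 1.03 (94.2%) | 1.13 (91.7%) | 1.28 (87.5%) |

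**Second set: logit scale.** 80% success for a typical trainee, intercept SD 1.0, mean device effect zero on the logit scale, effect SD 0, 0.5 or 1.0; simulated with 20,000 runs per setting and a pooled two-proportion test. At effect SD 1.0 the trainee-specific risk difference has an SD of about 0.16 and the marginal success rates are 76.1% and 73.5%. The formula can therefore be set beside the simulation: 2[0.761 × 0.239 + 0.735 × 0.265] = 0.753 and 0.16² = 0.0256, so the ratio is √(1 + 0.0256(m−1)/0.753).

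| Trainees × cases | N | Ratio at SD 1.0, formula | Ratio at SD 1.0, simulated | Rejection at nominal 5%, SD 0 / 0.5 / 1.0 |
|---|---|---|---|---|
| 4 × 20 | 80 | 1.28 | 1.30 | 5.1 / 7.3 / 13.3% |
| 8 × 10 | 80 | 1.14 | 1.15 | 5.3 / 6.0 / 9.4% |
| 6 × 40 | 240 | 1.52 | 1.55 | 4.9 / 9.7 / 21.7% |
| 20 × 4 | 80 | 1.05 | 1.05 to 1.07 | 5.2 / 5.4 / 6.7% |
| 40 × 2 | 80 | 1.02 | below 1.05 | 5.6 / 5.6 / 6.3% |

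The rejection rates at SD 1.0 are not pure type I error. A zero mean on the logit scale leaves a marginal difference of 76.1 − 73.5 = 2.6 points, so the pooled difference is truly non-zero. Centring on that difference lowers 8 × 10 from 9.4% to 8.6% and 6 × 40 from about 22% to 21%. The SD ratios are free of this and are the better measure.

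**If arms were balanced within trainee** (not stated in Section 2), the excess becomes [sb²(m−2) − 4sa²]/N. The case-level interval is then too narrow only if sb²(m−2) > 4sa². With sa = 0.10, 10 × 10 and sb = 0.05: 0.0025 × 8 = 0.02, less than 0.04, so the ratio is √(1 − 0.02/0.675) = 0.985 and the interval is slightly too wide. With 5 × 20 and sb = 0.15 the ratio is √(1 + 0.365/0.675) = 1.24.

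**The case against.** The strongest reply is that the plan promises no interval, p-value or pooled analysis, so there is no stated error bar to call wrong. This stands as to what is written: the case-level comparison is inferred from the absence of a trainee column and of any analysis method. It does not remove the point, because a file without a trainee identifier supports no other comparison.

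Second, the premises are assumed. Repeated cases per trainee are likely but not stated, and nothing in the documents shows that the device effect varies. With 20 trainees of 4 cases or 40 of 2, equally compatible with the plan, the understatement is minor even at a logit SD of 1.0. The largest ratio needs 240 cases from six trainees, which is large for a self-described pilot. All of this stands and fixes the lower end of the range near zero.

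Third, generalising to all trainees is a choice of target that the plan does not state formally. For a conclusion limited to the participating residents, the case-level comparison is adequate. This also stands; Section 1 only suggests the wider aim.

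A reader might go further and infer that repeated cases per trainee invalidate the comparison in themselves, or that the interval is too narrow whenever the effect varies. The documents support neither. Individual randomisation removes the effect of skill differences, and the second inference fails with one case per trainee, with arms balanced within trainee and modest effect variation, or with inference confined to the participants.

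**Conclusion.** The point holds in conditional form. What the documents establish is that the primary endpoint is trainee performance, that no trainee identifier is collected, and that the analysis section gives the trainee no role. Clustering therefore cannot be examined, and the between-trainee variation wanted for a later sample size cannot be estimated.

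The effect on precision depends on quantities the plan does not give. Under the assumptions shown, with 80 to 240 cases, the true SD is between about 1.0 and 1.5 times the pooled standard error. It is near 1.0 when trainees are many with few cases each or the effect is constant, about 1.3 for 4 trainees × 20 cases, and about 1.5 for 6 × 40, the last two at a logit effect SD of 1.0. These figures apply to allocation that ignores the trainee and to inference about trainees generally. They do not show that this trial's interval will be materially wrong. They show that it could be, and that the file as designed would not reveal it.

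**What to change.** - Add a coded trainee number to the worksheet and keep it when the data go to SPSS. Section 3 describes that transfer as "Following removal of patients' identifiable information except for age and the date of procedure"; say there that the trainee code is retained. It should be recorded from the first case, because this worksheet offers no way to reconstruct it.
- In Section 3, state that the difference in success will be reported with a trainee-clustered interval, for example cluster-robust with a small-sample correction, alongside the case-level interval.
- Report the number of trainees, cases per trainee overall and by arm, and, where estimable, the between-trainee variation in success and in device effect.

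The cost is one column and a few lines of text, with no extra patients. The clustered interval will be wider, and less stable if few trainees take part, which is why both intervals should be shown.

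Making a t interval on within-trainee differences, or a logistic model with a random device effect, the primary analysis is a real trade-off. With 20 trainees of 4 cases and coin-toss allocation, a trainee has cases in both arms with probability 1 − 2(½)⁴ = 0.875, so all 20 do in 0.875²⁰, about 7% of trials (about 9% in simulation); trainees with one arm only drop out of the t interval. With 4 × 20 and no effect variation, the t half-width averages 0.26 against 0.18 pooled. A random-effect model on a handful of trainees would often be poorly identified.

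### Group I's time to intubation includes grading time that Group II's does not, and the single TTI field cannot separate it

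*Combined protocol and SAP*

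**What the plan says.** Section 2 (Subjects/Methods/Data Collection) lists TTI as a secondary outcome. The clock runs over "the time it lapse from the reaching to the laryngoscope device until the time the trachea is intubated" and tube placement has been verified. No separate definition is given for either group.

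The same section adds a measurement in Group I. The grade of cord view "will be documented with direct laryngoscopy with Macintosh blade 3-4 before inserting Pneumoglide and after insertion of the device". For the control arm it states: "In group II, this variable will not be collected". Patients are those "assigned to be anesthetized by an anesthesia team that includes a PGY-2 or PGY-3 residents"; the plan does not say which team member does the grading.

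The data collection worksheet, printed under section 5, has one time field, "TTI: Time to intubate (minutes"). The grade fields, such as "PreLG: Laryngeal grade before insertion of Pneumoglide", hold a grade and no time. Attempts are recorded as "Att: Number of the attempts to successfully intubate", with no statement on whether a grading laryngoscopy counts as one.

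Section 3 gives no sample size or test, calls the study a pilot, and says that "the results obtained from this study can be used for sample size determination in future clinical trials".

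**The concern.** A time outcome compares two arms fairly only if the clock covers the same kind of activity in each. Here the protocol itself adds a measurement step to one arm. Device insertion is part of the Group I technique and belongs in its time. Grading the view is done for the study and does not.

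The plan leaves three things open: which reach for the laryngoscope starts the Group I clock, who grades, and whether the blade is withdrawn between grading and intubation. If teams answer differently, Group I time means different things from case to case. If all answer alike, the arm difference still mixes the device with grading time, with an airway preview, or with both. Randomization does not remove this and a larger sample does not dilute it. A time not marked during the case cannot be recovered. Should TTI later be used to size a trial, the problem carries forward, although section 3 names no outcome for that purpose.

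**Working it through.** The plan states no TTI value, SD, sample size or test, so there is no figure to reproduce. The check has two parts.

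**1. What the clock covers.** Notation, in seconds:
- D: true device effect on TTI (negative means faster)
- L: pre-device grading time
- p: pause for the post-device grade
- v: time saved by a preview of the airway (zero if there is none)
- b: reach and blade insertion lost when the first interval is subtracted and the blade was not withdrawn

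Expected arm difference, Group I minus Group II:
- Clock starts at the reach for the grading look (literal reading): D + L + p − v
- Clock starts at a later reach: D + p − v
- All grading time subtracted, blade withdrawn: D − v
- All grading time subtracted, blade not withdrawn: D − v − b

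The post-device grade comes after insertion and before intubation, so p is inside the clock on every reading. No line equals D unless further conditions hold. The worksheet records only the total, so neither of the last two lines can be computed from the planned data.

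Do the total and the subtracted estimate enclose D? Take a true 15 s saving (D = −15) and L = 15, with the clock at the first reach and the blade withdrawn:
- v = 0, p = 5, only the first look subtracted: total −15 + 15 + 5 = +5; subtracted −15 + 5 = −10. The range +5 to −10 misses −15.
- v = 0, p = 5, both grading times subtracted: +5 and −15. The range just reaches −15.
- v = 20, p = 0: total −15 + 15 − 20 = −20; subtracted −15 − 20 = −35. The range misses −15.

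If only the first look is subtracted, the pair encloses D when p ≤ v ≤ L + p. If both are subtracted, the condition is 0 ≤ v ≤ L + p. If the clock starts after the look, it narrows to 0 ≤ v ≤ p. None of these quantities is known.

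**2. How large the effect could be.** All inputs are assumed: no device effect, a net delay d = L + p − v, equal SDs and a two-sided 5% test of two means.

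SE = SD × √(2/n); chance of a significant difference = Φ(d/SE − 1.96) + Φ(−d/SE − 1.96).

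For n = 30 per arm, SD = 30 s, d = 15 s: SE = 30 × √(2/30) = 7.75; d/SE = 1.94; Φ(−0.02) + Φ(−3.90) = 0.49. A simulation with lognormal times (mean 60 s, SD 30 s) and a t-test gives 0.495.

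| n per arm | SD (s) | d = 5 s | d = 10 s | d = 15 s | d = 20 s |
|---|---|---|---|---|---|
| 20 | 40 | 7% | 12% | 22% | 35% |
| 30 | 30 | 10% | 25% | 49% | 73% |
| 50 | 20 | 24% | 71% | 96% | 99.9% |

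If laryngoscopy is continuous and noting a grade adds only 2 to 5 s, the middle row gives 6% (d = 2: d/SE = 0.26) to 10%. If a preview saves 10 s of a 15 s look and p = 0, then d = 5 s and the rate is again 10%. A preview that fully offsets the grading time gives d = 0 and 5%.

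**The case against.** The strongest reply is that this is one secondary outcome in a pilot. The excess may be only a few seconds, and a preview may cancel it. The documents name no test, so rejection rates describe an analysis that the plan does not specify, and one sentence defining the clock start might be enough. Most of this stands. It limits the severity and makes the rates illustrations only. It does not remove the point: a pilot can accept imprecision, but what Group I time measures is itself undefined. Defining the start alone would also leave the post-device pause inside the clock and unrecorded.

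Collecting the same pre-device grade in Group II would equalise the look and any preview. It would also add a study procedure to the control arm, and the post-device grade would still have no counterpart. That is for the sponsor to weigh.

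Three stronger readings are tempting, and the documents support none of them:
- *TTI is biased against the device.* The literal clock adds time to Group I, but a preview could offset or exceed it, and a later clock start would leave out the look.
- *The primary endpoint is compromised, or is certainly safe.* Trainee success does not use the clock. If the trainee grades, a preview could still affect success, the number of attempts and requests for faculty help. With the grader unstated, neither conclusion follows.
- *Estimates with and without grading time must bracket the device effect.* They do so only under the conditions shown in the working.

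**Conclusion.** The point holds. On a literal reading, Group I TTI includes the pre-device grading look; on every reading it includes any pause for the post-device grade. Group II TTI includes neither, and the planned worksheet cannot separate this time afterwards. An arm difference in TTI therefore cannot be read as the device effect alone.

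Net size and direction are unknown. The figure of about 49% for an uncompensated 15 s delay rests wholly on the assumed 30 per arm, SD 30 s and grading time. Over the assumed grid, the same delay gives 22% to 96%, and a delay of a few seconds gives little more than 5% at 30 per arm. The defect in definition is certain from the text; its practical effect is not. Severity is low to moderate.

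**What to change.** In section 2, state:
- which reach for the laryngoscope starts the Group I clock, relative to the pre-device grading look;
- who grades, and whether the blade is withdrawn after the look;
- that device insertion stays in Group I time;
- that the grading look is not counted in #Att.

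On the worksheet, record TTI in seconds. Add an entry for the time spent on pre-device grading and for any pause for the post-device grade, made by whoever already records TTI.

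In section 3, report the arm difference in TTI with a confidence interval twice: with total time, and with the grading time that falls inside the clock removed. Describe the pair as a sensitivity analysis, not as guaranteed bounds. State that removing grading time does not remove any airway preview. State also that, if the blade is not withdrawn, removal may take out reach and blade insertion that Group II time includes. If the trainee grades, note the possible preview when interpreting success, attempts and faculty help.

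The cost is a few sentences, one or two extra entries per Group I case, and two TTI estimates that may disagree. The entries must be made during the case, so the change is needed before data collection.
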